9 EFFICACY ANALYSES

9.1 Primary Efficacy Analyses

9.1.1 Primary Analysis

Haemoglobin (Hb) concentration will be summarised at screening (Visit 1), pre-randomization at Visit 2 (baseline assessment), and at each visit over the Treatment Period. Hb concentration (Observed Cases [OC]) will be summarised for the ITT (post hoc table 14.2.1.1) and re-evaluated PP (post hoc table 14.2.1.2) populations using descriptive statistics by visit for each treatment arm and overall. A scatterplot of Hb concentrations (OC) at each visit versus baseline will be presented by treatment arm for the re-evaluated PP population (post hoc figures 14.2.1.4, 14.2.1.5.1, 14.2.1.5.2, 14.2.1.6, 14.2.1.8, 14.2.1.10, 14.2.1.12.1, 14.2.1.12.2).

A dichotomous variable, representing response status in the degree to which Hb increases relative to baseline, will be calculated for each visit over the Treatment Period. Those subjects with at least 2g/dL increase in Hb from baseline or who

have normalization of Hb from baseline (≥ 12.0 g/dL for women, ≥ 13.0 g/dL for men) will be classified as "Hb responders". [*Post-hoc change from > 12.0 g/dL for women or > 13.0 g/dL for men*]. A shift from baseline of anaemic to non-anaemic status (ie Hb concentration shift from below to within the normal limits will be classified as "Hb normal limit responders". [*Post-hoc change to align Hb normal limit responder definition with the definition given in section 2*]. Patients who are normal at baseline cannot be classified as a responder. Ferric maltol patients who take IV Iron cannot be classified as responders after the intake of IV iron.

The null hypothesis for the primary efficacy endpoint analysis is that the proportion of Hb responders at Week 12 in the ferric maltol treatment arm is at least 20% lower than the proportion of Hb responders at Week 12 in the IV Iron treatment arm (i.e., ferric maltol is inferior to IV Iron for rate of Hb response at Week 12). The alternative hypothesis is that the proportion of Hb responders at Week 12 in the ferric maltol treatment arm is not worse than 20% lower than the proportion of Hb responders at Week 12 in the IV Iron treatment arm (i.e., ferric maltol is non-inferior to IV Iron for rate of Hb response at Week 12).

The proportion of Hb responders at Week 12 will be compared between the two treatment arms, by calculating a 2-sided confidence interval for difference in the proportions of Hb responders (risk difference) between the two treatment arms and comparing the lower confidence limit of this CI to the pre-specified non-inferiority margin. The CI will be calculated using the Delta Method approach [1] based on a logistic regression model, adjusted for treatment arm, baseline Hb (below the observed median or at least the observed median), and IBD subgroup (UC or CD). Note: For the CI calculation in the primary efficacy endpoint, the risk difference model was applied in the original analysis for CSR v1.0. The analysis method will be corrected to the Delta Method approach in the current post hoc analysis.

Post-hoc change: Note that missing values for the Hb responder status at Week 12 primary efficacy analysis will be imputed using a multiple imputation (MI) approach for ITT population. Missing values of Hb concentration at Week 12 will be imputed using the SAS[®] procedure MI. This will generate 20 complete datasets containing imputed values of Hb concentration at Week 12 for those missing in the original dataset. Variables considered helpful in guiding this imputation are deviation of baseline (Visit 2) Hb concentration from response threshold, deviation of Week 4 Hb concentration from response threshold, gender and IBD subgroup. A separate model will be computed for each treatment arm.

The Week 12 imputed value will then be back transformed from the Week 12 deviation from the response threshold.

Each model, corresponding to a given endpoint analysis, will be fitted against each of the imputed datasets. The SAS[®] procedure MIANALYZE will then be used to combine the individual analysis results for the given endpoint into one result.

The null hypothesis for the primary efficacy analysis will be rejected (i.e., ferric maltol will be deemed non-inferior to IV Iron), if the LCL of the 95% CI for the

difference (ferric maltol – IV Iron) in proportions of Hb responders at Week 12 is $\geq -20\%$ for both the ITT analysis and the re-evaluated PP analysis. The p-value in testing the aforementioned hypotheses will be equal to one minus the confidence coefficient corresponding to the CI for the risk difference whose LCL equals -20% (i.e., inverting the CI for the risk difference to a test statistic and calculating the p-value from the test statistic).

The proportion of Hb responders will be summarised for the ITT and re-evaluated PP populations using descriptive statistics by visit over the Treatment Period for each treatment arm and overall, utilizing all available Hb responder data (i.e., OC approach). Each summary will also present the proportion of Hb responders for the Week 12 visit (MI) using descriptive statistics, and will include the corresponding logistic regression model adjusted difference in the proportions of Hb responders between the two treatment arms, the corresponding adjusted 95% CI for the difference in proportions, and the adjusted p-value from testing the null hypothesis of inferiority in risk difference with non-inferiority margin 20%. Finally, each summary will also present the estimated logistic regression model adjusted odds ratio of Hb responder at Week 12 (MI) between the two treatment arms and corresponding 95% CI for the odds ratio (post hoc tables 14.2.2.1 and 14.2.2.2). A bar plot of the Hb responder rate will be presented by visit (OC) and treatment arm for each assessment for the re-evaluated PP population (post hoc figure 14.2.1.6).

9.1.2 Sensitivity Analysis

Two sensitivity analyses will be performed for the primary efficacy endpoint; in addition, three post-hoc sensitivity analyses will be performed using the re-evaluated PP population.

9.1.2.1 Observed Cases (OC) Analysis

The first sensitivity analysis will include all available assessments of Hb responder and will not exploit imputation of missing Hb responder status (i.e., only Observed Cases [OC] of Hb responder status are considered here). The primary efficacy endpoint analysis will be repeated using the OC approach for the ITT population. The proportion of Hb responders at Week 12 (OC) will be summarised using descriptive statistics for each treatment arm and overall. The summary will include the corresponding logistic regression model adjusted difference in the proportions of Hb responders (risk difference) between the two treatment arms, the adjusted 95% CI for the difference in proportions, and the adjusted p-value from testing the null hypothesis of inferiority in risk difference with non-inferiority margin 20%. The summary will also include the estimated adjusted odds ratio of Hb responder at Week 12 (OC) between the two treatment arms and corresponding 95% CI for the odds ratio. (post hoc table 14.2.2.1)

9.1.2.2 Observed Cases (OC) Repeated Measures Analysis

The second sensitivity analysis for the primary efficacy endpoint will be performed on the ITT and re-evaluated PP populations, in which Hb responder status will be

analysed in a longitudinal analysis using a repeated measures generalized linear mixed model (GLMM) approach (i.e., a repeated measures logistic regression approach) for all available assessments of Hb (i.e., only Observed Cases [OC] of Hb responder status are considered here) over Visits 2 (Day 0; baseline) to 4 (Week 12).

Post-hoc change: The approach will fit a logistic model to the Hb responder dependent variable, where an unstructured working correlation structure will be specified for each arm (e.g., by way of the appropriate random statement within the GLIMMIX SAS® procedure) to model the within-subjects correlation of repeated Hb responder status at Visits 3 and 4. If the model fit fails to converge, an autoregressive(1) structure will be specified. If this also fails to converge, alternative working correlation structures will be examined. Covariates of the GLMM will include the fixed effects of treatment, baseline Hb (below the observed median or at least the observed median), IBD subgroup, visit as a categorical variable, and treatment-by-visit interaction. The estimated adjusted odds ratio for treatment effect, and its corresponding 95% CI, from the model will be presented by visit.

To assess the sensitivity of Hb responder status over time – by way of a general linear model (GLM) approach – separate logistic regression models will be fitted to the Hb responder dependent variable at each visit during the Treatment Period up to Week 12, using all available assessments of Hb (i.e., only Observed Cases [OC] of Hb responder status are considered here). Each model will include terms for the effects of treatment, baseline Hb (below the observed median or at least the observed median), and IBD subgroup. The estimated adjusted odds ratio for treatment effect, and its corresponding 95% CI, will be presented for each model (i.e., by visit). Sensitivity of Hb responder status over time will be assessed by comparing these by-visit treatment effect odds ratio estimates from the logistic regression models (the GLMs) to those obtained from the GLMM model. (post hoc tables 14.2.2.3 and 14.2.2.4)

9.1.2.3 Week 12 compliance analysis

Post hoc change: The first post-hoc sensitivity analysis will be performed on the mPP compliance population (post hoc table 14.2.2.5). The analysis performed will be the same as for the primary efficacy. This analysis is relevant to HEOR and more of the real-world interpretation of the data. In addition, a waterfall plot of overall compliance in the first 12 weeks based on this subset of patients will be included (post hoc figure 14.3.2.3).

9.1.2.4 Week 12 non-windowed analysis

Post hoc change: The second post-hoc sensitivity analysis will be performed on the mPP windowing population (post hoc table 14.2.2.6). Patients will be considered as a responder if they have a haemoglobin response at any point up to and including Week 12 visit. The analysis performed will be the same as for the primary efficacy.

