2.3 Study Endpoints

2.3.1 Primary Efficacy Endpoint

The primary efficacy endpoint is the proportion of subjects achieving either a $\geq 2\text{g/dL}$ increase in Haemoglobin (Hb) OR normalization of Hb ($>12\text{g/dL}$ for women, $>13\text{g/dL}$ for men) at Week 12.

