5 ANALYSIS POPULATIONS

For details of the randomized, safety, and ITT populations, refer to Statistical Analysis Plan v3.0, dated 14 February 2019, Section 5.1 to 5.3.

For details of the PP population, refer to Statistical Analysis Plan v3.0, dated 14 February 2019, Section 5.4 and Section 8 below. To clarify, data of the subjects with major protocol deviations occurring after Week 12 were excluded from the PP analysis of the long-term endpoints from that point of deviation onwards in the original analysis for CSR v1.0.

Patients data are re-evaluated with a focus on visit window, drug compliance, missing data, and the allowance of immunosuppressants. A re-evaluated PP population is defined for the post hoc analyses.

Two sensitivity PP population will be determined for the analysis of the primary efficacy data:

The modified PP population for compliance (mPP compliance) contains all patients from the re-evaluated PP population, along with all patients who are only excluded from the re-evaluated PP population due to compliance issues.

The modified PP population for windowing (mPP windowing) contains all patients from the re-evaluated PP population, along with all patients who are only excluded from the re-evaluated PP population due to Week 12 windowing issues for haemoglobin.

Data of the subjects with major protocol deviations occurring after Week 12 are excluded from the re-evaluated PP analysis of the long-term endpoints from that point of deviation onwards.

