8 STUDY POPULATION

For details of the listings and summaries for the study population, refer to Statistical Analysis Plan v3.0, dated 14 February 2019.

In addition to the existing categories described in Statistical Analysis Plan v3.0, dated 14 February 2019, additional major protocol deviations include the following categories:

- Repeated non-compliance in self-administration of ferric maltol study drug, where non-compliance is less than 80% or greater than 120% of expected administration of study drug in the first 12 weeks. Where data were missing the compliance may be assessed based on individual visit pill returns, where data exists the compliance would be based on the average compliance in the first 12 weeks of study.
- Subjects that had a Week 12 haemoglobin value measured more than 2 weeks (+/- 14 days) outside the planned Week 12 assessment, ie an additional 1 week window beyond the 1 week window in the schedule of assessments.
- IV Iron subjects who did not follow the specific country dosing regimens. An IV iron dose up to Week 12 that was ≥ 2 or $\leq .5$ times the calculated dose based on weight and Hb and per the local Prescribing Information, will not be included in the re-evaluated PP population.
- Immunosuppressant use will not be a criterion for exclusion from the re-evaluated PP population, based on protocol version 6, dated 11 July 2017.

Protocol deviations deemed to be major, but not recorded on the database, will be included by means of a spreadsheet which will be agreed by Shield and Clinipace based on the minutes of the subject evaluability meeting.

No imputation was performed for missing data in compliance calculations.

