A sensitivity analysis will be performed on the mPP windowing population containing all patients from the re-evaluated PP population, along with all patients who are only excluded from the re-evaluated PP population due to haemoglobin windowing issues will be included. Patients will be considered as a responder if they have a haemoglobin response at any point up to the Week 12 visit. The analysis performed will be the same as for the primary efficacy.

A sensitivity analysis will be performed on the re-evaluated PP population. Patients will be included into subgroups based on the protocol version they first consented under (prior to version 6, version 6 onwards). The analysis performed for each subgroup will be the same as for the primary efficacy.

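### The Week 12 windowing sensitivity analysis changes the responder rule as well as the population, so table 14.2.2.6 cannot show what the visit-window exclusion did

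*SAP*

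**What the plan says.** The primary comparison in section 9.1.1, in both SAP v3.0 and the post-hoc SAP, is of status at one visit: "The proportion of Hb responders at Week 12 will be compared between the two treatment arms". The lower limit of the 95% confidence interval is held against a 20-point margin.

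Section 8 of the post-hoc SAP adds a major deviation that removes subjects from the re-evaluated PP set: "Subjects that had a Week 12 haemoglobin value measured more than 2 weeks (+/- 14 days) outside the planned Week 12 assessment". Section 5 then defines the mPP windowing population as the re-evaluated PP set plus "patients who are only excluded from the re-evaluated PP population due to Week 12 windowing issues for haemoglobin".

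Section 9.1.2.4 analyses that population and changes the scoring: "Patients will be considered as a responder if they have a haemoglobin response at any point up to and including Week 12 visit". It continues: "The analysis performed will be the same as for the primary efficacy". The result goes to post hoc table 14.2.2.6. The re-evaluated PP primary result is in table 14.2.2.2.

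**The concern.** The mPP windowing population differs from the re-evaluated PP set only in the subjects excluded for Week 12 timing. The natural use of an analysis in it is to see whether that exclusion matters, and for this the population should be the only thing that changes.

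Here the endpoint changes too, and for all subjects, including those whose Week 12 sample was on time. Post-hoc section 9.1.1 derives responder status at every treatment-period visit, so a subject who responds at Week 4 and has lost the response at Week 12 moves from failure to success. The 20-point margin, which SAP v3.0 section 4 sets for the Week 12 responder rate, is then applied to a different quantity.

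At stake is the reading of one sensitivity table. If it agrees with the re-evaluated PP result, it may be cited as showing that the window exclusion is harmless. If it disagrees, the window may be blamed. Neither inference would be sound.

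**Working it through.** **1. What changes between the tables.** Let D(population, rule) be the ferric maltol minus IV iron difference. Then

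D(mPP windowing, any time) - D(re-evaluated PP, at Week 12) = [D(mPP windowing, at Week 12) - D(re-evaluated PP, at Week 12)] + [D(mPP windowing, any time) - D(mPP windowing, at Week 12)].

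The first bracket is the effect of the window exclusion and the second is the effect of the new rule. Both need D(mPP windowing, at Week 12), which no planned output gives. By contrast, the compliance analysis in section 9.1.2.3 changes only the population.

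**2. Is the any-time rule needed to use the added subjects?** No. Under section 8 they are excluded because a Week 12 haemoglobin was measured at the wrong time, so a value exists.

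**3. Effect on each arm's rate.** Within one population, P(any time) = P(responder at Week 12) + P(responder earlier but not at Week 12). The last term is zero or positive, so the rate can only stay or rise.

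**4. The design figure.** SAP v3.0 section 4 gives 75% in both arms, margin 20 points, 90% power, a two-sided 95% interval and 108 per arm.
- Without continuity correction: 2 × 0.75 × 0.25 × (1.960 + 1.282)² / 0.20² = 98.5.
- With it: (98.5/4) × (1 + √(1 + 4/(98.5 × 0.20)))² = 108.3. This matches 108, although strict rounding up gives 109.
- 108 × 1.12 = 120.96, which gives the stated 121.

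The point does not depend on this. It supplies 108 per arm for the illustration.

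**5. Effect on the arm difference.** The document gives no rates of lost response, so 0 to 10% per arm is assumed. The interval is an unadjusted Wald one, which approximates the planned delta-method interval: LCL = d - 1.96 × √[(pF(1-pF) + pI(1-pI))/108]. For 65% against 75%: -0.10 - 1.96 × √(0.415/108) = -0.221.

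| Week 12 rate, ferric maltol / IV | Earlier response lost, ferric maltol / IV | Any-time rate, ferric maltol / IV | Difference (points) | LCL (points) |
|---|---|---|---|---|
| 65 / 75% | 5 / 0% | 70 / 75% | -10 → -5 | -22.1 → -16.9 |
| 75 / 75% | 0 / 10% | 75 / 85% | 0 → -10 | -11.5 → -20.6 |
| 75 / 75% | 5 / 5% | 80 / 80% | 0 → 0 | -11.5 → -10.7 |
| 75 / 75% | 10 / 10% | 85 / 85% | 0 → 0 | -11.5 → -9.5 |

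In the first row a failed comparison passes, and in the second a passed one fails. With equal loss the limit still moves, because the variance falls as the rates rise.

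**6. How the two effects can hide each other.** Take assumed counts in one arm: 81 of 108 respond at Week 12 (75.0%). Adding five out-of-window non-responders gives 81/113 = 71.7%, a window effect of -3.3 points. If four of the 113 had an earlier response that was lost, the any-time count is 85/113 = 75.2%. Table 14.2.2.6 would look unchanged from table 14.2.2.2 although the exclusion mattered.

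**The case against.** The strongest reply is that nothing depends on this table. Post-hoc section 9.1.1 rests non-inferiority on the ITT and re-evaluated PP analyses alone. Table 14.2.2.6 is one of three added sensitivity analyses, is labelled post hoc, and states its rule openly. All of that stands, so a reader should not infer that the trial's conclusion is compromised.

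Second, the document never says what the analysis is for, and there is other evidence on the window. ITT includes all randomized subjects, and SAP v3.0 section 7.2 presents values by nominal visit. Out-of-window Week 12 values therefore appear to enter the ITT analyses under the unchanged rule. This stands in part: the window question is not wholly unanswered, but the direct comparison with the re-evaluated PP set is missing.

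Some stronger readings are tempting but not supported:
- *The any-time rule favours one arm.* If IV iron is assumed to act faster (Week 4/Week 12 response of 50%/75% for IV iron and 20%/75% for ferric maltol, latent correlation 0.5 to 0.85), a zero difference becomes -4.8 to -1.1 points. Other assumptions push it the opposite way, as the table of scenarios shows, and the document supplies none of these rates.
- *The Week 12 value itself might be dropped*, because section 12 reads "Patients will be considered as a responder if they have a haemoglobin response at any point up to the Week 12 visit". That is a summary of changes, and the operative text in section 9.1.2.4 includes the Week 12 visit.
- *Extra unscheduled blood draws give extra chances to respond.* Section 9.1.2.4 does not mention unscheduled values. SAP v3.0 section 7.2 uses them only where a window has no nominal assessment, while section 7.3 counts them among observed cases. The point is left open.
- *Late visits gain extra time because of the new rule.* The extra time comes from admitting out-of-window visits and would remain under any scoring.

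**Conclusion.** The point holds in a limited form. Section 9.1.2.4 alters population and endpoint together, describes the result as the primary analysis, and leaves no output that separates the two effects. A difference between tables 14.2.2.6 and 14.2.2.2, or the lack of one, cannot be attributed to the visit window, and responses lost by Week 12 are credited as successes. This follows from the text and needs no assumed figure.

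Only the upward effect on each arm's rate, within a given population, is certain. Under assumed lost-response rates of 0 to 10% per arm, the arm difference shifts by up to 10 points in either direction, half the margin. The table remains readable as a disclosed ever-response analysis, so calling it meaningless would go too far. It does not isolate the window exclusion.

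**What to change.** In post-hoc section 9.1.2.4, and to match in section 12, analyse the mPP windowing population with the primary definition: responder status from the haemoglobin at the nominal Week 12 visit, whatever its actual date. Population is then the only difference from table 14.2.2.2.

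If ever-response is of interest, report it as a separately labelled descriptive row without the 20-point margin test, and state whether unscheduled values count. Add a note that out-of-window subjects have longer or shorter follow-up than planned, since the change does not remove that.

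The cost is a wording change in two sections and one rerun of table 14.2.2.6, with no new data.

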9.1.2.5 Week 12 immunosuppressant analysis

Post hoc change: The third post-hoc sensitivity analysis will be performed on the re-evaluated PP population. Patients will be included into subgroups based on the protocol version they first consented under (prior to version 6, version 6 onwards) (post hoc table 14.2.2.7). The analysis performed for each subgroup will be the same as for the primary efficacy.

9.2 Secondary Efficacy Analyses

9.2.1 Secondary Analysis

9.2.1.1 Key Secondary Endpoints

The change from baseline (CFB) in Hb concentration at Week 12 (MI) secondary endpoint will be analysed for the ITT population using an analysis of covariance (ANCOVA) model.

The ANCOVA model will have terms for treatment arm, baseline Hb (below the observed median or at least the observed median), and IBD subgroup. The treatment effect of ferric maltol compared to IV Iron will be considered using differences of adjusted means. No formal statistical significance level in the treatment comparison will be defined, as the p-value from the ANCOVA model will be presented for descriptive purposes only. A summary of CFB in Hb concentration (OC) will be provided using descriptive statistics for each visit over the Treatment Period by treatment arm and overall. The summary will include the following ANCOVA model estimates: adjusted means (i.e., Least-Square Means [LSMs]) of CFB in Hb concentration at Week 12 for each treatment arm, the difference in treatment arm LSMs, the corresponding 95% CIs for treatment arm specific LSMs and difference in treatment arm LSMs, and the p-value for the difference in treatment arm LSMs (post hoc table 14.2.2.1). Mean CFB in Hb concentration will be plotted against visit (OC) by treatment arm for the re-evaluated PP populations (post hoc figures 14.2.1.5.1 and 14.2.1.5.2).

A dichotomous variable, representing status of Hb concentration relative to the normal limits of Hb will be calculated for each visit over the Treatment Period. Female subjects with Hb concentration greater than or equal to 12 g/dL and male subjects with Hb concentration greater than or equal to 13 g/dL will be classified to be within normal limits of Hb [*Post-hoc change from >12.0 g/dL (females) or >13.0 g/dL (males)*]. Those subjects with a shift from baseline of anaemic to non-anaemic status (ie Hb concentration shift from below to within the normal limits will be classified as "Hb normal limit responders". [*Post-hoc change to align Hb normal limit responder definition with the definition given in section 2*]. Subjects missing Hb concentration at Week 12 will be assumed to have Hb concentration not within normal limits (i.e., these subjects will be considered Hb normal limit non-responders). The logistic regression modelling and hypothesis testing for the primary analysis (Section 9.1.1) will be repeated here for the Hb normal limit responder at Week 12 secondary endpoint.

A summary will be provided for the Hb normal limit responder secondary endpoint using descriptive statistics by visit over the Treatment Period for each treatment arm and overall, utilizing all available Hb data (i.e., OC approach). The summary will also present the Hb normal limit responder rate for the Week 12 visit (MI) for ITT population using descriptive statistics, and will include the corresponding logistic regression model adjusted difference in proportions of Hb normal limit responders between the two treatment arms, the corresponding [Delta Method derived] adjusted 95% CI for the difference in proportions, and the p-value from testing the null hypothesis of inferiority in risk difference with non-inferiority margin 20%. Finally, the summary will also present the estimated logistic regression model adjusted odds ratio of Hb normal limit responders at Week 12 (MI) between the two treatment arms and corresponding 95% CI for the odds ratio (post hoc tables 14.2.4.1 and 14.2.4.2).

Note: For the CI calculation in the secondary efficacy endpoints, the risk difference model was applied in the original analysis for CSR v1.0. The analysis method will be corrected to the Delta Method approach in the current post hoc analysis.

